9.2.2 Study population

The study cohort will include all patients who initiate Tiotropium/Olodaterol (Tio/Olo) or Tiotropium (Tio) during the patient selection period. Initiation (new use) will be determined based on no prescription claims for Tio/Olo or Tio during the baseline period or during all available data prior to cohort entry date. All patients will additionally be required to have a second claim for the index medication within 60 days after cohort entry to ensure primary adherence of index therapy.

The following exclusion criteria will then be applied to generate the unmatched cohort:

- Aged <40 years on cohort entry.

[figure not shown]
Proprietary confidential information © 2020 Boehringer Ingelheim International GmbH or one or more of its affiliated companies

- Any LAMA, LABA, ICS maintenance therapy (alone or in combination) during the 180-day baseline period prior to cohort entry for maintenance treatment and not cough, i.e. duration >30 days, or any prescription within the 30 days prior to cohort entry.
- Patients without continuous enrolment (days since first inpatient/outpatient encounter in the data) during the baseline period.
- No prior diagnosis of COPD [ICD-10: J41*, J43*, J44* and doubt (UTAGAIFLG) = 0 (no)]
- Patients without a second prescription claim of their index medication within 60 days after the cohort entry date.
- Diagnosis of asthma [ICD-10: J45* and doubt (UTAGAIFLG) = 0 (no)] during the baseline period.
- Diagnosis of lung cancer [ICD-10: C34*, D02.2, Z80.1, Z85.1 and doubt (UTALAIFLG) = 0 (no)] or lung transplant (Health claim code: 150317670, 150322510, 150322610, 150336510, 150336610, 150336710, 150399270) prior to the cohort entry date using all available data.
- Patients who initiate both Tio/Olo and Tio simultaneously on the cohort entry date.
- Any use of triple therapy (LAMA + LABA + ICS) during the baseline period or between the cohort entry date and 1 day prior to the start of follow-up.

All patients will be selected into the first treatment arm (Tio/Olo or Tio) that they qualify for and will not be allowed to re-enter the cohort by design.

The cohort will then be used to construct two matched cohorts (not mutually exclusive) according to the: 1) basic propensity scores and 2) high dimensional propensity scores

Figure 2 Depicts the flow diagram of patients.

Basic Propensity Score Matching

Basic propensity score will be used to assess comparative effectiveness between the two exposure groups. The basic propensity score will be estimated using logistic regression with Tio/Olo treatment as the outcome and the following variables determined *a priori* as predictors:

a) predefined demographic variables (measured at time of cohort entry):

- Age
- Sex
- Calendar Year of Index
- Hospital Size (as a proxy for urban/rural)

b) all concomitant medications and comorbidities/conditions/other variables enumerated in [Section 9.3.3.](#)

The final basic propensity score will then be used to identify one initiator of *Tiotropium* for each initiator of *Tiotropium/Olodaterol* with the same propensity score (\pm a caliper of 5%) (**Austin 2011**).

High Dimensional Propensity Score Matching

In addition to the basic propensity scores, high dimensional propensity score (hdPS) analysis will also be used to assess comparative effectiveness between the two exposure comparison groups. hdPS is a modification of traditional propensity scores that incorporate additional steps for empirical variable selection. Briefly, hdPS includes additional covariates by ranking a complete list of available variables of a given attribute (e.g. all ICD-10 codes) based on prevalence, recurrence, association between covariate and exposure, and association between covariate and outcome, and then including the top covariates in that list in the propensity score prediction. This technique has been shown to produce improved effect estimates compared to using all predefined covariates in the propensity score prediction (**Schneeweiss 2009**).

The set of covariates to estimate the propensity scores will include the same predefined covariates as in the basic propensity scores (categories a and b), but also an empirically chosen set of covariates (category c):

a) predefined demographic variables (measured at time of cohort entry):

- Age
- Sex
- Calendar Year of the Cohort Entry Date
- Hospital Size (as a proxy for urban/rural)

b) all concomitant medications and comorbidities/conditions/other variables enumerated in [Section 9.3.3.](#)

c) The top variables (number of variables determined by the [REDACTED]) chosen by the hdPS algorithm described above. The following attributes will be used to select variables eligible for hdPS analysis:

- Disease Data – ICD-10 Codes
- Inpatient ACT – Health Claim Code
- Outpatient ACT – Health Claim Code
- Lab Data – Laboratory Code

In selecting diseases eligible for hdPS, the ICD-10 code will be truncated after the dot. Importance of variables will be ordered using the bias ranking method. Health service intensity variables will also be

used. Health service intensity variables are calculated for each attribute by counting the total number of codes for each patient, counting the number of distinct codes for each patient, and creating eight binary variables representing the quartiles for both the total number of codes and number of distinct codes. Along with the binary variables created for each code, the eight binary intensity variables are used in the hdPS algorithm resulting in 2000-8000 binary variables total depending on the attributes selected.

Logistic regression conditional on the final set of covariates will be used to compute the propensity to initiate *Tiotropium/Olodaterol* versus *Tiotropium* given all the variables in a, b, and c above. The final hdPS will then be used to identify one initiator of *Tiotropium* for each initiator of *Tiotropium/Olodaterol* with the same propensity score (\pm a caliper of 5%) (Austin 2011).

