9.3.3 Covariates

The covariates listed below consist of demographics, medications, comorbidities, and other variables that are hypothesized to confound the relationship between exposure and outcome. Covariates will be identified based on data recorded within 180 days prior to or on the index date (date of

dispensing/initiation of the exposure), unless otherwise specified. If multiple measurements are made in the baseline period, then the most recent measurement will be used.

There is an additional variable for “doubt diagnosis” related to each disease diagnosis. Only confirmed diagnoses will be used for all disease variables (this represents ~95% of all diagnoses).

Absolute and relative frequencies of each covariate will also be reported. Detailed descriptions of the listed covariates can be found in Annexes 2 and 3. The measure definitions for diagnoses are subject to modification to further incorporate disease codes/names as deemed appropriate upon further exploration of the data during study implementation.

Demographics (last recorded)

- Age
- Sex
- Year of Cohort Entry
- Hospital Size (as a proxy for urban/rural).

Concomitant Medications

- Oral/Injected Corticosteroids
- Short acting beta agonist (SABA) (number of claims)
- Short acting muscarinic antagonist (SAMA) (number of claims)
- Systemic Xanthines
- Systemic Antileukotrienes
- Interleukin Inhibitors for Asthma
- Non-steroidal Respiratory Anti-inflammatories
- Opioids/Narcotics
- Systemic Antihistamines
- Oral Antibiotics for a Respiratory Condition (number of claims)
- Cough and Cold Preparations
- Diabetes Mellitus Medications, excluding Insulin
- Insulin
- Cytostatics
- Antirheumatics, Biologic
- Antirheumatics, Non-Steroidal
- Antithrombotic Agents
- Lipid-lowering Agents
- Antihypertensives/Diuretics
- Antiepileptics/Psycholeptics/Psychoanaleptics
- Antipsoriatics
- Antivirals
- Thyroid Therapies
- Vaccinations

[Antibiotics + Respiratory diagnosis, [REDACTED] can try to find antibiotics specific to respiratory conditions]

Comorbidities/Symptoms

- COPD Exacerbations (number of exacerbations)
- All-Cause Hospitalization
- Hospitalization due to Respiratory Condition
- Acute Myocardial Infarction, AMI
- Angina Pectoris
- Peripheral Vascular Disease, PVD
- Heart Failure, HF

- Hypertension
- Cardiac Arrhythmias
- Cerebrovascular Disease
- Any Cancer (except nonmelanoma skin cancer)
- Allergic Rhinitis
- Chronic Sinusitis
- Bronchiectasis
- Pneumonia
- Chronic Bronchitis

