9.4 DATA SOURCES

The proposed study will utilize data from Medical Data Vision (MDV).

MDV is an electronic, record-based healthcare database that spans from April 1, 2008 to 31 March 2019, and contains 25.1 million observable patients. It contains patient-level information on demographics, diagnoses and prescription information from 374 medical facilities across Japan. The distribution of patients in the database is similar to that of the national demographics for patients seeking healthcare, although the MDV database has more elderly and sicker patients.

The Japanese health care structure enables anyone to seek medical treatment at any facility of their choosing, including hospitals. Thus, acute hospitals in Japan consist of both primary (outpatient) and secondary (inpatient) care facilities. In fact, the MDV database is built out of more than 80% outpatient data, which allows for identification of patients who visit hospitals without severe conditions. These hospitals follow a diagnosis procedure combination (DPC) billing structure unique to Japan that enables capture of inpatient discharge summary

information (disease name, operations, adjuvant treatment, etc.), health claims for procedures (surgery information, departments, wards, etc.), and health claims for treatments (medications, medical devices, devices, etc.). A smaller subset of consenting hospitals also provide data on blood test results.

Thus, it is expected that 1) patients with COPD in these hospitals provide a good representation of the general Japanese COPD population; and 2) data from patients treated in the different hospitals cannot be linked. Due to the nature of the database, inclusion criteria to ensure that the patients are treated for COPD in the same hospitals continuously are defined as described in [Section 9.2.2](#).

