9.6 DATA MANAGEMENT

Dataset

The Medical Data Vision dataset is comprised of administrative records of longitudinal inpatient, outpatient and drug data from multiple hospitals that have been standardized and de-identified prior to use for the analysis. The statistical analysis will be conducted using the

COPD Maintenance Therapy Drug Duration

Given limited information on treatment duration in the MDV data, a days supply of 14 days will be assumed for “Spiolto Respimat 28puffs.” Otherwise, 30 days will be assumed for all LAMA, LABA, and ICS maintenance therapies, including “Spiriva Inhalation Capsules 18microg”, “Spiriva 2.5microg Respimat 60puffs 150microg”, “Spiriva 1.25microg Respimat 60puffs 75microg”, and “Spiolto Respimat 60puffs”. A grace period of 14 days between assumed end of days supply and subsequent prescription will be used as an allowable gap.

Handling of Missing Data

Missing data that occurs in covariates or descriptive variables will be classified as its own level (i.e. missing data indicator). In addition, a feasibility assessment before beginning the

analyses will be done, and variables with >75 % missing values will be excluded from all analyses, other than baseline characteristics. If a variable is left with only one level other than missing, the variable will be excluded completely from all analyses.

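### The washout admits some recent LAMA, LABA or ICS users, and that prior use is neither forced into the propensity scores nor tabulated by arm

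*Combined protocol and SAP*

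**What the plan says.** Three parts of the protocol have to be read together.

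- **Eligibility (9.2.2).** For the index drugs the look-back is strict: "no prescription claims for Tio/Olo or Tio during the baseline period or during all available data prior to cohort entry date". For other LAMA, LABA or ICS use it is looser. Use in the 180-day baseline excludes a patient only if it is "for maintenance treatment and not cough, i.e. duration >30 days, or any prescription within the 30 days prior to cohort entry". Triple therapy during baseline, or between cohort entry and the day before follow-up starts, also excludes.
- **Assumed supply (9.6).** Apart from one 28-puff pack, "30 days will be assumed for all LAMA, LABA, and ICS maintenance therapies". Also: "A grace period of 14 days between assumed end of days supply and subsequent prescription will be used as an allowable gap". Neither section says whether the 30-day limit applies to one continuous episode or to the sum over the baseline.
- **Covariates (9.2.2, 9.3.3, 9.7.1.1).** Apart from demographics, the pre-specified predictors in both scores are "all concomitant medications and comorbidities/conditions/other variables enumerated in" Section 9.3.3. The inhaled bronchodilators listed there are short-acting only, for example "Short acting beta agonist (SABA) (number of claims"; LAMA, LABA and ICS do not appear. Section 9.7.1.1 reports the Section 9.3.3 variables and their standardized differences. The hdPS adds empirically ranked codes from several attributes, one of which is "Outpatient ACT – Health Claim Code".

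The limitations section (9.9) mentions maintenance therapy taken before the baseline period, but not use inside it. Section 9.12 accepts that the two groups of initiators may differ in severity and clinical course.

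**The concern.** The outcome is built from the same three drug classes as the washout. A patient who has already had a LAMA, a LABA or an ICS may be more severe, or closer to triple therapy, than one who has had none. Prior use could also differ by arm: a patient stepping up from another LAMA might tend to start Tio/Olo, while an earlier LABA/ICS user who adds a LAMA might tend to start Tio. Under Section 9.3.2.1, a single LAMA with LABA/ICS for 30 consecutive days counts as triple therapy. In that second patient, a LABA/ICS prescription at the same visit as the second Tio prescription would give an event dated to the first day of follow-up.

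These routes are plausible, not documented. If prior use were unequal between the matched arms, the hazard ratio would be shifted and no planned table would reveal it.

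**Working it through.** **1. Who passes the washout.** Inputs: 30-day supply and 14-day allowable gap (9.6); limit of more than 30 days in 180, and no prescription on days -30 to -1 (9.2.2). A prescription on day d covers days d to d+29. Another joins the same episode if at most 14 uncovered days lie between, that is, if it falls no later than d+44. At d+45 the gap is 15 days and a new episode starts.

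| Prior prescriptions (day relative to entry) | Total assumed supply | Limit read per episode | Limit read cumulatively |
|---|---|---|---|
| One, day -30 | 30 days | Excluded (last 30 days) | Excluded (last 30 days) |
| One, day -31 | 30 days (days -31 to -2) | Enters | Enters |
| Two, days -75 and -31 (44 apart) | 60 days | Joined, excluded | Excluded |
| Two, days -76 and -31 (45 apart) | 60 days | Two 30-day episodes, enters | Excluded |
| Four, days -180, -135, -90, -45 | 120 days | Four 30-day episodes, enters | Excluded |

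One isolated prescription on days -180 to -31 passes under both readings. Repeated prescriptions pass only under the per-episode reading.

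**2. Whether the analysis handles it.** The basic score has no LAMA, LABA or ICS term. The hdPS forces in the same list, so it has no such term by design, though it may select one. Section 9.7.1.3 fits the primary Cox model in both matched cohorts. The balance table follows the Section 9.3.3 list, so prior use is not shown for either.

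**3. Possible size, with assumed inputs.** The documents give neither the prevalence of prior use by arm nor its effect on the outcome. For a binary confounder with prevalence pA in Tio/Olo and pB in Tio, and outcome rate ratio r, the hazard ratio is multiplied approximately by

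B = (1 + pA(r-1)) / (1 + pB(r-1)).

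The plan states its hazard ratio as 1.7 (abstract) or 1.73 (9.5), Tio over Tio/Olo. Inverted, 1/1.70 = 0.588.

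| Assumed pA vs pB | Assumed r | B | 0.588 becomes | Arms swapped |
|---|---|---|---|---|
| 5% vs 2% | 1.5 | 1.025/1.010 = 1.015 | 0.597 | 0.579 |
| 10% vs 5% | 2 | 1.10/1.05 = 1.048 | 0.616 | 0.561 |
| 10% vs 5% | 3 | 1.20/1.10 = 1.091 | 0.641 | 0.539 |
| 20% vs 5% | 3 | 1.40/1.10 = 1.273 | 0.748 | 0.462 |

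These factors assume that no proxy and no hdPS-selected code absorbs any of the difference.

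**4. Room for a fix.** The plan's size figures reproduce closely. Schoenfeld's formula for 1:1 groups, 4(1.960+1.282)²/(ln 1.73)², gives 140 events against the stated 141. With the hazard ratio implied by 6% and 10%, ln(0.90)/ln(0.94) = 1.703, it gives 149 events; 149/0.08 = 1863 patients against the stated 1856. The 1856 patients are 928 pairs. Section 9.5 counts 1,829 Tio/Olo users, so 1 - 928/1829 = 49% could be lost before pairs run short, if every remaining user is matched. That count lists only the 30-day part of the washout, so the true starting number may be lower.

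**The case against.** The strongest case on the other side has four parts.

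- **Short courses are admitted on purpose.** The criterion separates maintenance treatment from a course for cough. This stands: letting one short course in is a design choice. It does not explain why that use is left out of the scores and the balance table.
- **The hdPS can find it.** Section 9.4 says the data include "health claims for treatments (medications, medical devices, devices, etc", so drug codes appear to be eligible, and the algorithm ranks codes partly by association with exposure and outcome. A strong confounder is a natural candidate. This stands in part: selection is possible but not guaranteed, it works on individual codes rather than classes, and the basic-score cohort does not benefit.
- **Proxies are forced in.** Both scores contain SABA and SAMA claims, oral or injected steroids, xanthines, exacerbations and respiratory hospitalization. These should absorb part of any severity difference, which the factors above ignore.
- **The LABA/ICS route is narrow in the main analysis.** There can be no prescription in the last 30 days, no baseline asthma diagnosis, and no triple therapy in baseline or before follow-up starts. This largely stands. What remains is a patient whose LABA/ICS resumes at or after the second index prescription.

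A reader might also infer that a prescription on days -44 to -31 is still current at entry, so that the washout should be 44 days. The documents do not support this. The 14 days are an allowable gap between two prescriptions, not supply. A day -31 prescription runs out on day -2, so the 30-day window already agrees with Section 9.6.

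**Conclusion.** The concern holds in a limited form. The rule admits patients with an isolated LAMA, LABA or ICS prescription on days -180 to -31 and, under one reading of an undefined term, patients with up to four. That use is not a pre-specified predictor in either score and would not appear in the balance table. Given the endpoint, it is a plausible confounder that should be pre-specified.

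Two stronger conclusions are tempting but not supported. One is that repeatedly treated patients definitely enter: under the cumulative reading, two prescriptions already exclude. The other is that a confounder differing between arms remains in the primary comparison: no figure in the documents shows an imbalance, its direction or its effect. Nor does the plan claim that patients are naive to all maintenance therapy; it claims new use of Tio or Tio/Olo. The factor of 1.015 to 1.27, in either direction, rests wholly on assumed prevalences (5% vs 2% up to 20% vs 5%) and rate ratios (1.5 to 3). Annexes 2 and 3, which hold the covariate details, are not in the text reviewed.

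**What to change.** 1. Add baseline LAMA, LABA and ICS use to Section 9.3.3, by class, as the number of prescriptions in the 180 days and the days since the last one. It then enters both propensity scores and the standardized-difference table. Code patients with no prior use as their own level, not as missing. Otherwise the Section 9.6 rule that drops variables with more than 75% missing values could remove the new items.
2. State in Section 9.2.2 that the limit of more than 30 days means total assumed supply over the 180-day baseline, and say whether days covered by two classes at once count once or twice. The 30-day window before entry can stay as it is.

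The cost is a few extra covariates (at most six: three classes by two measures) from data that must be queried for the exclusion anyway. The cumulative definition may exclude a small number of patients, and matching on more terms may lose a few pairs. The required 141 events and 1856 patients do not change.

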Patients with uncontrolled COPD experiencing exacerbations may escalate to triple LAMA/LABA/ Inhaled Corticosteroids (ICS) therapy (**Vogelmeier 2017**). According to prior COPD guidelines, ICS can be used for frequent exacerbations, but the most recent GOLD guidelines recommend that ICS only be used for Asthma-COPD-overlap patients (**Vogelmeier 2017**). However, in the DYNAGITO study, the prevalence of LAMA/LABA/ICS (triple therapy) at baseline was 40.8% in moderate to very severe COPD patients in Japan (**Calverley 2018, Ichinose 2018**). ICSs may lead to several minor and major complications. The side effects of ICS treatment can range from weight gain and local side effects, such as pneumonia, oral candidiasis and dysphonia, to adrenal suppression, cataracts, and osteoporosis (**Tariq 2016, Wilkie 2015**). In addition, patients with low blood eosinophil counts may not respond to ICS (**Hizawa 2015**).

Several clinical trials have shown that new LAMA/LABA inhalers could better manage patients, potentially reducing the use of ICS as part and parcel of maintenance therapy in COPD (**Magnussen 2014**). However, the evidence obtained from previous clinical trials is not always reflected in clinical practice, and there is limited research from real world settings

that show LAMA+LABA combination therapy provides more benefit than LAMA monotherapy in Japanese patients with COPD. Therefore, real world evidence from Japanese COPD patients is crucial in addressing this gap in knowledge. It is also essential to understand real world treatment patterns and outcomes, in particular, escalation to triple therapy as a proxy for worsening COPD condition.

Spiolto® Respimat®, a combination of Olodaterol (a LABA) and Tiotropium (a LAMA) (herein referred to as Tio/Olo) was approved in September 2015 in Japan. Spiriva® Respimat®, a Tiotropium (a LAMA) monotherapy (herein referred to as Tio), was approved in October 2004 and widely used in Japan. Both maintenance therapies are available, but real world evidence is lacking if one therapy is superior to the other, and whether it can prolong the duration to triple therapy that includes ICS.

This study aims to evaluate the time to escalation to triple therapy among the Japanese COPD patients newly initiating therapy with Tio or Tio/Olo using real world data.

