9.2 SETTING

9.2.1 Definitions

Study Period: the entire period of time that includes the baseline period, the cohort entry date (index date), and follow-up period for the study population. The study period will be from **01 April 2015** (180 days prior to Spiolto approval date of 28 September 2015 in Japan) to **31 March 2019** (end of available data).

Patient Selection Period: the period of time for which patients are eligible to enter the cohort. The earliest date of the patient selection period is **28 September 2015**, (the Spiolto approval date in Japan). The latest date of the patient selection period is 31 December 2018, corresponding to 90 days before the end of available data (31 March 2019), ensuring that all patients have at least 60 days after the cohort entry date to identify a second prescription for index therapy and at least 30 days to be capable of the 30-day overlap to determine the triple therapy initiation outcome.

Cohort Entry Date: Date of entry to the initial cohort of Tio/Olo vs. Tio users (*first prescription*).

Baseline Period: the 180-day period that ends 1 day prior to the cohort entry date used to assess covariate information. The earliest start of the baseline period would be 01 April 2015, corresponding to 180 days prior to the approval date of Spiolto.

[figure not shown]
Follow-Up Period: the period starting at the second prescription for Tio/Olo or Tio within 60 days of the cohort entry date (first prescription) and ending at the earliest occurrence of the outcome (use of triple therapy), or the first occurrence of inpatient death, disenrollment, or end of the study period (31-Mar-2019). A sensitivity analysis will employ an as-treated censoring approach to further censor upon discontinuation of index therapy or initiation of the other index treatment arm. Patients may have different lengths of follow-up (i.e. variable follow-up).

Since health care is nationalized in Japan, the notion of enrollment is not applicable. Therefore, a proxy enrolment criterion defined as start of enrolment = date of first inpatient/outpatient encounter; end of enrolment = date of last inpatient/outpatient encounter will be used. “Enrolment” herein will refer to this proxy enrolment measure. For entry into the study population, patients will be required to have had at least 180 days of enrollment prior to the cohort entry date.

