9.7.3 Sensitivity Analyses

1. Less Stringent Qualifying Event Criterion

Instead of defining the event to qualify patients for inclusion based on two prescriptions within 60 days, patients may enter upon only one prescription. While some confidence is lost in whether the patients truly took their index medications, the less stringent qualifying event criterion will allow more patients to be included, increasing statistical power. Furthermore, the possibility of immortal time bias is also mitigated, since the time between prescriptions is no longer present.

2. As-treated Censoring

The analysis will use an as-treated approach for primary, secondary and further endpoint outcomes. In addition to the censoring criteria mentioned for the intention-to-treat approach (outcome, death, or end of data), patients will also be censored after medication discontinuation or switching over to the other arm.

3. Alternative algorithm for COPD

The analysis will use a different set of diagnosis codes for COPD (J43*, J44*) when selecting COPD patients. Compared to the primary analysis, this algorithm omits the diagnostic code for chronic bronchitis (J41*), as this code is commonly used by pulmonologists when prescribing Mucodyne to patients who do not actually have chronic bronchitis. While some true chronic bronchitis patients may be excluded, the selection of patient will increase specificity.

4. Asthma patients with doubt

Asthma patients with doubt are defined as patients with a diagnosis code for asthma and without evidence of any asthma specific treatment (ie., ICS, ICS/LABA). This sensitivity analysis will include patients identified with asthma with doubt.

5. ACOS sensitivity analysis

Patients that have evidence of asthma during the follow-up period will have their data censored on the date of asthma diagnosis during the follow-up period. This will ensure that they contribute information during their COPD disease trajectory up until the time they develop asthma. This approach will mitigate introducing immortal time bias for those patients with ACOS during the follow-up period.

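### Asthma coded on the entry date, between the first and second fills, or only before day −180 is neither excluded nor a predefined propensity-score covariate; the resulting bias cannot be sized from the documents

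*Combined protocol and SAP*

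**What the plan says.** - **Exclusion (Section 9.2.2, repeated in the abstract).** Patients are removed for "Diagnosis of asthma [ICD-10: J45* and doubt (UTAGAIFLG) = 0 (no)] during the baseline period". Section 9.2.1 defines the baseline period as "the 180-day period that ends 1 day prior to the cohort entry date".
- **Cohort entry (Section 9.2.1).** "Date of entry to the initial cohort of Tio/Olo vs. Tio users", that is, the first prescription.
- **Follow-up (Section 9.2.1).** It is "the period starting at the second prescription for Tio/Olo or Tio within 60 days of the cohort entry date".
- **Asthma-censoring analysis (Section 9.7.3, item 5).** Patients with evidence of asthma in follow-up "will have their data censored on the date of asthma diagnosis during the follow-up period". The primary analysis has no asthma censoring.
- **Other windows in the same list (Section 9.2.2).** Triple therapy is excluded in the baseline period and also "between the cohort entry date and 1 day prior to the start of follow-up". Lung cancer and lung transplant are checked "prior to the cohort entry date using all available data".
- **Covariates (Section 9.3.3).** Asthma is not listed. The covariate window covers the 180 days before the index date and the index date itself.
- **Outcome (Section 9.3.2.1).** Each qualifying form of triple therapy contains an ICS.

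**The concern.** Three kinds of patient with a confirmed asthma code can enter the primary cohort:

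- (a) asthma is coded at the visit where the index inhaler is first prescribed;
- (b) asthma is first coded between the first and second fills;
- (c) asthma was coded only before the 180-day look-back, for example seven months before entry.

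This matters because of how the endpoint is read. Section 7 treats escalation to triple therapy as a sign that COPD is getting worse, and it also says that "the most recent GOLD guidelines recommend that ICS only be used for Asthma-COPD-overlap patients". Section 9.7.3, item 4, counts ICS and ICS/LABA as asthma-specific treatment. A patient who starts an ICS for asthma can therefore be counted as a COPD escalation. If such patients are spread unevenly over the arms after matching, the primary hazard ratio is affected.

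**Working it through.** **1. Reproduce the plan's own dates.**

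- Latest start of follow-up: 31 December 2018 + 60 days = 1 March 2019, as Figure 1's footnote states.
- Earliest baseline start: 28 September 2015 − 180 days = 1 April 2015, as Section 9.2.1 states. That baseline runs to 27 September 2015.

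So the windows are being read as the plan intends.

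**2. Lay the asthma windows end to end.** Day 0 is cohort entry and g is the day of the second fill, at most 60.

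| Day of asthma code | Excluded? | Censored in item 5? |
|---|---|---|
| before −180 | no | no |
| −180 to −1 | yes | not applicable |
| 0 to g−1 | no | no |
| g onward | no | yes |

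The uncovered interval after entry is g days: 30 days for a fill on day 30, and 60 days at the limit.

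**3. Number affected.** The documents give no asthma coding rate. Purely as an assumption, if 1% to 5% were coded in the interval, the counts before matching would be:

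- Tio/Olo: 0.01 × 1,829 ≈ 18 to 0.05 × 1,829 ≈ 91
- Tio: 0.01 × 13,132 ≈ 131 to 0.05 × 13,132 ≈ 657

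**4. What would drive the effect.** Take the 1-year rates in Section 9.5 (6% and 10%, ratio 0.60) as the rates without asthma. Let a be the share of asthma patients in an arm and e their 1-year escalation risk. Arm risk = (1 − a) × base + a × e. Both a and e are assumptions; neither is in the documents.

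| a (Tio/Olo, Tio) | e = 20% | e = 50% |
|---|---|---|
| 3%, 3% | 6.42/10.3 = 0.62 | 7.32/11.2 = 0.65 |
| 5%, 2% | 6.7/10.2 = 0.66 | 8.2/10.8 = 0.76 |
| 2%, 5% | 6.28/10.5 = 0.60 | 6.88/12.0 = 0.57 |

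The ratio can move either way or hardly at all, depending on two unknowns. The table shows the dependence and is not an estimate of bias.

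**The case against.** The windows themselves are hard to dispute. The case against lies in the consequence, and much of it stands.

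- **ICS exclusion.** Section 9.2.2 removes maintenance LAMA, LABA or ICS use of more than 30 days in the baseline period, and any such prescription in the last 30 days. A type (c) patient therefore had no sustained ICS maintenance for about six months, so a very high escalation risk is hard to assume. This stands for (c).
- **Triple-therapy exclusion.** Patients who step up to triple therapy before the second fill are already removed. This stands in part, because it can act unequally. Adding a single-agent ICS makes a Tio/Olo patient a triple-therapy user, while a Tio patient given the same drug is on two classes and stays.
- **High-dimensional score.** ICD-10 codes truncated after the dot are candidates. If the Section 9.3.3 window applies, J45 on the entry date is eligible. Selection is not guaranteed, and (b) and (c) lie outside that window.
- **Item 5 on repeated codes.** A code entered again after the second fill triggers censoring. That helps only from the later date, and only in that sensitivity analysis.
- **Item 4.** It deliberately adds patients with an asthma code and no asthma treatment, so it partly tests the effect of admitting similar patients. It also shows that the plan regards an untreated code as doubtful, so these patients should not all be called known asthmatics.
- **Different purposes.** Triple therapy is the outcome, so patients must be free of it at the start of follow-up. A 180-day asthma look-back is not wrong merely because that criterion runs longer.

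A reader might infer that the primary hazard ratio is biased, or diluted to a figure such as 0.65 or 0.76. The documents do not support this: those figures need an assumed prevalence and an assumed 50% escalation risk. Nor does Section 7 say that ICS use implies asthma. It also mentions frequent exacerbations under prior guidance and reports 40.8% triple therapy at baseline among Japanese patients in one COPD trial.

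**Conclusion.** The gap is real and follows from the text alone. Confirmed asthma coded from the entry date to the day before the second fill (up to 60 days), or only before day −180, is not screened and is not a predefined covariate in either propensity score. Because every outcome route contains an ICS, some of these patients may escalate because of asthma, and the existing criteria cover this only in part. The size and direction of any bias cannot be computed from the documents. The point therefore rests on the windows and on the composition of the endpoint, not on a numerical estimate.

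A reader might also conclude that the primary exclusion should simply be extended to the day before follow-up, as for triple therapy. That goes too far. Although it would create no immortal time, it would exclude on diagnoses made after exposure has begun. Poor response to one drug could prompt an asthma work-up, so the exclusion could act differently by arm.

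**What to change.** 1. In Section 9.2.2 and the abstract, extend the confirmed-asthma exclusion to the baseline period plus the cohort entry date.
2. Add confirmed asthma before the baseline period, from all available data, as a covariate in both the basic and the high-dimensional score. State that look-back varies between patients beyond the guaranteed 180 days.
3. Extend item 5 of Section 9.7.3 so that patients with confirmed asthma coded after entry and before the second prescription are removed at the start of follow-up.
4. As a further sensitivity analysis, repeat the primary hazard ratio without patients who have the earlier asthma history.

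Together, steps 1 and 3 reduce the uncovered interval after entry to zero days in the asthma sensitivity analysis. In the primary analysis, days 1 to g−1 stay open by choice.

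The cost is one changed date condition, one covariate, an extended sensitivity analysis and one more model run. The downsides are slightly fewer patients, unequal look-back for the history covariate, and possible arm-dependent selection from the post-entry screen. The last is why that screen belongs in a sensitivity analysis.
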